Does VeraFlo with Prontosan® decrease time to wound and fracture healing in patients with infected lower extremity fractures with indwelling hardware?

Principal Investigator: [name]

Sponsor:

University of Missouri
Orthopaedic Surgery
[name]
[contact]
[name]

Funding Company: KCI USA, Inc.

Hypothesis: Prontosan instillations will decrease time to wound and fracture healing and decreases bacterial load.

Null Hypothesis: Prontosan instillations do not decrease time to wound and fracture healing and decrease bacterial load.

Background: Surgical site infections (SSIs) are a devastating and relatively common surgical complication, occurring in 2% to 5% of patients undergoing surgery in the United States. SSIs can significantly increase patient morbidity, hospital stay duration, healthcare costs, and patient mortality (Anderson 2011). Negative Pressure Wound Therapy (NPWT) with Vacuum-Assisted Closure (VAC) is an established adjunctive treatment option for open wounds that offers the ability to promote healing. However, there is limited evidence for its utility with active infections. Wounds that are acutely infected or that contain an adherent biofilm present a challenging problem (Kim et al 2015).

Wound VAC therapy involves cleaning the wound, applying a custom-fit foam to cover the wound, placing a transparent drape over the wound and adjacent skin, and attaching tubing to connect the foam to a VAC suction canister. NPWT is achieved with a pulling force supplied by the VAC suction canister. Typically, suction will remain at a constant pressure until the dressing is removed. Continuous VAC therapy was recently reported to be more effective than standard moist wound care in surgical site infection after ankle surgery (Zhou et al. 2015). VAC therapy with instillations is a novel treatment option that provides the combination of negative pressure with intermittent instillation of a solution. Polihexanide (Prontosan®) is a modern antiseptic that combines a broad antimicrobial spectrum with low toxicity, high tissue compatibility, no reported adsorption and good applicability as solution, gel, ointment, foam and in wound

dressings. Unlike other antiseptics, the antimicrobial efficacy of Prontosan® is not impaired in human wound fluid, human tissue or by high loads of blood or albumin. Furthermore, Prontosan® blocks the microbial attachment to surfaces and has been shown to effectively remove biofilms in vitro and in vivo (Hubner *et al* 2010).

Study Recruitment: 20 subjects, not including screen failures. The small sample size will serve as a pilot study to determine an adequately powered study after completion.

Study Design: The objective of this study is to determine if Prontosan instillations (in conjunction with NPWT treatment) decrease time to wound and fracture healing and decrease bacterial load compared to NPWT treatment without Prontosan.

With IRB approval, up to 30 patients will consent and enroll, with a goal of 20 completed subjects. Patients with infected lower extremity wounds, status-post ORIF, undergoing standard of care operative debridement will be enrolled and randomized to either the VeraFlo with Prontosan group or standard negative pressure group. There will be 10 patients in each group. The standard negative pressure group will receive the V.A.C Ultra Negative Pressure Wound Therapy System. NPWT device settings for both arms will be 125mmHg. The following setting will be used for the VeraFlo group: Prontosan, 20min dwell time 2 hour cycle. The amount of Prontosan to be infused is based on the size of the wound and will vary between subjects.

Subject weight, BMI, comorbidities, and smoking status will be collected from the medical record and/or the subject, and will be used for research purposes.

All NPWT dressings will be applied sterilely in the OR after debridement and irrigation per standard of care practice. Only the standard negative pressure device or Veraflo dressing may be used on enrolled participants (based on randomization designation), without any silver dressing, Adaptec or Xeroflo. Dressings will be changed every 72 to 96 hours (based on patient progress and clinical presentation) in the OR for a minimum of 1 more debridement (indicating at least one debridement and NPWT application).

Bacterial load (organism quantities are listed as scant, moderate, or heavy), identification of organism, and susceptibility will be analyzed and reported by the University of Missouri Hospital Laboratory, via semiquantitative wound culture(s) done at each debridement procedure. A maximum of 3 wound cultures will be used for the purposes of research, and the sponsor will cover the cost of up to 3 wound cultures. The culture will be done in the OR, after negative pressure dressing removal, prior to surgical prepping.

The subject will sign consent, be enrolled, and then be randomized at the pre-operative/screening visit. During the initial surgical debridement procedure, information about the wound characteristics, the wound culture results, and information about the dressing that is placed in the OR will be collected for research purposes.

Wound healing will be evaluated at weekly intervals until the sutures are removed and the wound is deemed healed. To assess wound healing, weekly photos of the wound/incision will be done either in clinic, or will be obtained from the subject after they take the photo at home. When applicable, weekly phone visits will be completed to obtain a photo of the incision, (starting after discharge from the hospital), until the subject returns for their SOC clinic visit for suture removal (around 3 weeks post-op). The wound/incision will be assessed with a VAS Incision Healing Assessment Form.

Clinical follow-up visits will be standard after wound healing with clinical radiographs to document fracture healing--6 weeks after initial surgery (+/- 1 week), 3 months (+/-1 week), 6 months (+/-2 weeks), and 12 months (+/-2 weeks) or until fracture healing with minimum of 6 months f/u. Any further debridement or procedures done for fracture healing, including bone stimulator use, will be documented. A clinical photo(s) will be taken at all visits following the initial surgical debridement to document wound healing.

Primary Endpoints:

1. Time to wound and fracture healing (indicating successful resolution of infection)
2. Bacterial load (organism quantities are listed as scant, moderate, or heavy)

Secondary Endpoints:

Number of surgeries:

1. # of operative debridements until wound healed
2. # of surgeries for fracture healing (nonunion and bone grafting)
3. VAS (Incision Healing Assessment Form) scores, based on standardized digital image

Inclusion/Exclusion Criteria

Inclusion:

- Patients 18 years and older

- Patients who will be undergoing surgical management (including the use of NPWT therapy) of an infected lower extremity status-post open reduction and internal fixation (ORIF)

Exclusion:

- Pregnant females
- Incarcerated patients and those not able to give informed consent

Withdrawal of Subjects: Subjects will be informed that they have the right to withdraw from the study at any time for any reason, without prejudice to their medical care. The Investigator(s) may elect at any time to withdraw a subject from the study for any reason unrelated to the study if such a decision is in the subject's best medical interest. If a subject discontinues the study prematurely, or is withdrawn by the Investigator(s), as much follow-up data as possible will be obtained. The primary reason for termination or discontinuation will be documented in the report of the final results.

Safety:

Adverse Events:

If an AE/SAE occurs, the details will be collected on an AE/SAE form.

An adverse effect (AE) is any undesirable experience (e.g., sign, symptom, illness, clinically significant abnormal laboratory value, or other medical event) occurring in a subject during the course of the study, whether or not it is related to the investigational device or procedure.

An AE does include a/an:

- Exacerbation of a pre-existing illness
- Increase in frequency or intensity of a pre-existing episodic event or condition
- Condition detected or diagnosed after study device use even though it may have been present prior to the start of the study
- Continuous persistent disease or symptoms present at baseline that worsen following the start of the study

An AE does not include a/an:

- Medical or surgical procedure (e.g., surgery, endoscopy, transfusion); the condition that leads to the procedure is considered an AE

- Pre-existing diseases or conditions present or detected at the start of the study that do not worsen
- Situations where an untoward medical occurrence has not occurred (e.g., hospitalizations for cosmetic elective surgery, social and/or convenience admissions)
- The disease or disorder being studied, or sign or symptom associated with the disease or disorder, unless the disease, sign or symptom is more severe than expected based on the subject's condition and/or requires intervention.

Serious Adverse Events:

A Serious adverse event is an adverse event that:

- Led to death,
- Led to serious deterioration in the health of a subject that
 - resulted in a life-threatening illness or injury,
 - resulted in permanent impairment of a body structure or body function,
 - required inpatient hospitalization or prolongation of existing hospitalization, or
 - resulted in medical or surgical intervention to prevent permanent impairment to a body structure or a body function.
 - Led to fetal distress, fetal death or a congenital anomaly or birth defect.

The following clarifications are provided for the serious adverse events:

- Life-threatening means that the subject was, in the view of the Investigator, at immediate risk of death from the event as it occurred. The definition does not include an event that, had it occurred in a more severe form, might have caused death.
- Hospitalization for elective treatment of a pre-existing condition that did not worsen during the study is not considered a serious adverse event.
- "Inpatient" hospitalization means the subject has been formally admitted to a hospital for medical reasons. This may or may not be overnight. It does not include presentation at a casualty or emergency room.
- Important medical events that may not result in death, or be life-threatening, however based upon appropriate medical judgment, may jeopardize the subject and may require medical or surgical intervention to prevent one of the outcomes listed in this definition.
- Is significant for any other reason.

Anticipated Adverse Events:

Anticipated adverse events are those events that are reasonably expected to occur as a result of the subject's disease state or treatment. For this study, anticipated

adverse events associated with the procedure or post-procedure include, but are not limited to, the following;

- Infections, both deep and superficial
- Allergies or other reaction to device materials
- Temporary or permanent nerve damage as a result of pressure or hematoma.
- Cardiovascular complications including venous thrombosis, pulmonary embolism, and cardiac arrest.
- Wound hematoma and delayed wound healing.

Device-related adverse events are those events that can be directly attributed to the study device and are adjudicated as such by the Investigator. These events may include, but are not limited to:

- Infections, both deep and superficial
- Allergies or other reaction to device materials
- Loosening of the implant as a result of changed condition in load transfer, respectively fatigue wear or tissue reaction to implant or as result of inadequate anchoring technique.
- Dislocation, subluxation or inadequate scope of movement as a result of failure to achieve optimum positioning of the implant.
- Bone fractures as a result of one-sided overload or weakened bone structure.
- Temporary or permanent nerve damage as a result of pressure or hematoma.
- Wound hematoma and delayed wound healing.

Unanticipated Adverse Events:

An Unexpected Adverse Experience (UAE) is defined as any adverse reaction, the nature and severity of which is not consistent with the applicable product information. These events will be documented as described below.

An Unexpected Adverse Device Effect (UADE) is defined as any adverse effect on the study subject's health or safety, or any life-threatening problem or death caused by or associated with the device. Also, the effect must not have been previously identified in the Investigational Plan or Instructions for Use in its nature, frequency or severity. UADEs may also include other serious problems associated with the device that affect the rights or welfare of study subjects.

Adverse Event Documentation:

The Principal Investigator or designee will report adverse events for the study analysis. Adverse events will be evaluated and differentiated by:

- Severity of the event, defined below.

- Mild: Awareness of signs and symptoms, but easily tolerated; are of minor irritant type, causing no loss of time from normal activities; symptoms would not require medication or a medical evaluation; signs and symptoms are transient.
- Moderate: Discomfort severe enough to cause interference with usual activities; requiring treatment, but not extended hospitalization or intensive care for the subject.
- Severe: Incapacitating with inability to do work or usual activities; signs and symptoms may be systemic in nature or require medical evaluation and/or treatment; requiring additional hospitalization or intensive care (prolonged hospitalization).
 - Serious Code, as defined in Section “Serious Adverse Events”
 - Relatedness to the device or procedure, defined as:
 - Unrelated: AE is due to the underlying disease state or concomitant medication or therapy not related to the study-specific devices or procedures.
 - Probably not Related: AE had minimum or no temporal relationship to the study-specific devices or procedures and/or more likely alternative etiology exists.
 - Possibly Related: AE had a strong temporal relationship to the study-specific devices or procedures and alternative etiology is equally or less likely compared to the potential relationship to the study-specific devices or procedures.
 - Probably Related: AE had a strong temporal relationship to the study-specific devices or procedures and another etiology is unlikely.
 - Unknown: Relationship of the AE to the study-specific devices or procedures and alternative etiology is unknown.

Any severe adverse event or device related unanticipated advent must be reported to the study Sponsor by telephone or fax within 24 hours of the event. Additionally, the full details of the event will be documented in the study data base and with a follow up fax if the details of the event cannot be enter into the database promptly. Arthrex Inc. will submit the applicable reports required by each reviewing regulatory authority when appropriate.

Unanticipated Adverse Device Effect (UADEs):

A UADE is any SAE on health or safety or any life-threatening problem or death caused by, or associated with, a device, if that effect, problem, or death was not previously identified in nature, severity, or degree of incidence in the investigational plan or application (including a supplementary plan or application), or any other unanticipated serious problem associated with a device that relates to the rights, safety, or welfare of subjects (21 CFR 812.3).

Expectedness

All Serious Adverse Events will be assessed for expectedness based on the following definitions:

- Expected, Anticipated: the effect, problem, or death had been previously identified in nature, severity, or degree of incidence in the study or product documentation.
- Unexpected, Unanticipated: if that effect, problem, or death was not previously identified in nature, severity, or degree of incidence in the study or product documentation

UADE Reporting to KCI, USA Inc.

UADEs and SAEs must be reported by the Investigator to KCI and the reviewing Institutional Review Board (IRB) per their reporting requirements.

Risks Associated With NPWT Therapy/Dressing

Risks	Disorders/Conditions
Skin and Subcutaneous Tissue Reaction/Allergy	
• Desiccation/injury• Skin rash, irritation, blistering• Pruritus/itching• Skin excoriation/breakdown• Skin stripping• Skin scarring if significant skin irritation were to occur• Maceration• Skin hyper/hypo-pigmentation at and/or around dressing application area• Erythema/redness, edema, inflammation, or swelling at and/or around dressing application area
Mild Pain or Discomfort	
• Tenderness/minor ache at and/or around dressing application area• Perspiration associated with wearing dressing• Auditory irritation (due to mild buzzing sound of negative pressure unit)• Decreased sleep or sleep quality• Paresthesia (numbness, tingling, prickling, creeping sensation)

Other	
 • Bleeding • Cardiac compromise (vagal response, bradycardia) • Pulmonary compromise • Accidental instillation in a body cavity • Localized infection • Autonomic dysreflexia (in subjects with spinal cord injury) • Retained foreign debris (e.g.foam) in the wound • Impairment of mobility/activity (limitation secondary to weight and attachment of therapy unit) • Possible tubing entanglement/trip or slip hazard leading to fracture, tissue damage • Incorrect therapy unit settings resulting in incorrect frequency/dosing • Tunneling • Stalled healing/non-progression of healing • Deterioration of the wound • Systemic reaction (due to allergic reaction to dressing materials) • Burn secondary to therapy unit or power cord malfunction
-------	---

Prontosan:

In very rare cases there may be a mild burning sensation after Prontosan is applied. This should subside after a few minutes. In Rare cases (less than 1 out of 10,000), anaphylactic shock has been reported after the use of Prontosan. Protosan can also cause allergic reactions such as itching and rashes.

Quality Assurance of Data Collection:

Patient confidentiality is maintained by adherence to the rules of HIPAA and the University of Missouri IRB. Close assessment of perioperative events and complications will be performed to ensure no significant deleterious effects are resulting from research activity.

Statistical analysis plan:

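### Bacterial-load cultures follow Prontosan exposure in one arm only with no stated neutralisation, so any antiseptic carried into the specimen would look like a treatment effect on a primary endpoint

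*Protocol*

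**What the plan says.** All of this is in the Protocol.

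- **Endpoint.** The second item under Primary Endpoints is "Bacterial load (organism quantities are listed as scant, moderate, or heavy"). The Study Design objective is to learn whether Prontosan instillations "decrease bacterial load compared to NPWT treatment without Prontosan". The Statistical analysis plan section compares growth category between arms with a rank sum test at p < 0.05.
- **Sampling.** Study Design obtains the grades "via semiquantitative wound culture(s) done at each debridement procedure", with at most three cultures per patient used for research. It fixes the moment: "The culture will be done in the OR, after negative pressure dressing removal, prior to surgical prepping". It names no specimen type and no neutraliser, and does not ask for the time since the last instillation.
- **Exposure.** Study Design: "The following setting will be used for the VeraFlo group: Prontosan, 20min dwell time 2 hour cycle". Also: "The amount of Prontosan to be infused is based on the size of the wound and will vary between subjects". The control arm receives negative pressure without Prontosan.
- **Persistence.** The Background states that "the antimicrobial efficacy of Prontosan® is not impaired in human wound fluid, human tissue or by high loads of blood or albumin".
- **Order of events.** Study dressings are applied after debridement and irrigation, and changed in the operating room every 72 to 96 hours.

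**The concern.** The endpoint is meant to measure how many organisms are in the wound, but a culture measures how many grow after sampling. The two agree only if nothing in the specimen inhibits growth. In the VeraFlo arm the specimen may contain the antiseptic under test; in the control arm it cannot. Any such inhibition would therefore act on one arm and in one direction, towards Prontosan.

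A lower grade in the VeraFlo arm would then have two explanations, a real reduction in the wound or suppressed growth in the specimen, and the planned comparison could not separate them. This cannot be left to a statistical analysis plan: once the specimen has been collected, no analysis recovers the distinction. It also matters beyond this trial, because the pilot is meant to inform the size of a later powered study, and an inflated difference would carry over into that design.

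**Working it through.** **1. Which cultures are exposed.** The study dressing goes on after the initial debridement, so the culture from that procedure precedes any study Prontosan. If it counts among the maximum of three, at most 3 − 1 = 2 research cultures per VeraFlo patient are exposed. These later cultures are the ones that can show a treatment effect. The protocol does not say which culture supplies the endpoint.

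**2. How recent the exposure may be.** With a 2-hour cycle and no stated interval free of antiseptic before dressing removal, the last instillation could lie within roughly two hours of removal. Dwell takes 20/120 = 1/6 of the cycle, or 20/140 = 1/7 if the two hours exclude it. Suction applies for the rest and removes some fluid. The amount left at sampling is unknown, and because the instilled volume depends on wound size it would vary between patients.

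**3. Direction.** The Background says wound material does not impair the agent. If residue reaches the specimen in an active amount, it can only lower the VeraFlo reading.

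**4. Illustration of size.** The protocol gives no effect size, power or category rates, so there is no figure of its own to reproduce. The planned test was simulated with no true difference.

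- From the protocol: n = 10 per arm (N = 20), rank sum test, 0.05 level.
- Assumed: a two-sided test; four growth-category distributions; a share q of VeraFlo cultures reading one category too low (a reading in the lowest category cannot fall further); the analysed culture is a post-dressing one.
- Test statistic: z = (W − n(N+1)/2) / √V, where W is the rank sum of the control arm and r are the midranks. Here n(N+1)/2 = 10 × 21/2 = 105 and V = n²/(N(N−1)) × Σ(r − (N+1)/2)² = (100/380) × Σ(r − 10.5)². Reject if |z| > 1.96.
- 40,000 runs per setting.

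False-positive rate, with the part favouring Prontosan in brackets:

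| Assumed distribution | q = 0 | q = 25% | q = 50% | q = 75% | q = 100% |
|---|---|---|---|---|---|
| none/scant/moderate/heavy, equal | 4.8% (2.5) | 6.5% (5.4) | 11.1% (10.8) | 19.6% (19.5) | 32.3% (32.2) |
| same four, 10/30/30/30% | 4.9% (2.3) | 7.3% (6.6) | 15.3% (15.1) | 29.6% (29.6) | 50.7% (50.7) |
| same four, 40/30/20/10% | 5.1% (2.6) | 6.2% (5.2) | 10.7% (10.3) | 18.7% (18.5) | 30.8% (30.8) |
| scant/moderate/heavy, equal | 4.6% (2.3) | 6.8% (6.1) | 14.3% (14.1) | 27.8% (27.7) | 49.3% (49.3) |

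With no carryover the test holds its level (4.6% to 5.1%). At q = 50% the rate is 10.7% to 15.3%. The increase over q = 0 ranges from 10.7 − 5.1 = 5.6 points to 15.3 − 4.9 = 10.4 points. Between 10.3/10.7 = 96% and 15.1/15.3 = 99% of the false positives favour Prontosan.

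**The case against.** The strongest reply is that carryover is nowhere demonstrated. The Background statement concerns activity in the wound. It does not say that what remains after suction, then sampling and plating, still inhibits growth. That depends on residual concentration, specimen type and laboratory method. The hospital laboratory may already neutralise specimens under procedures that are not shown. This stands: the document supports only a conditional claim.

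Four stronger readings may tempt a reader and are not supported.

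- *The wound is full of Prontosan until the dressing comes off and is swabbed at once.* The protocol describes intermittent instillation with suction, does not time the last instillation, gives no interval between removal and sampling, and does not say that a swab is used.
- *All research cultures are affected.* The initial-debridement culture is not.
- *The bacterial-load result is biased by a known amount.* The share q is assumed. At 25% the rate moves only to 6.2% to 7.3%, and the largest figures require every VeraFlo reading to be shifted.
- *A saline rinse in both arms would be a neutral remedy.* The Background credits Prontosan with blocking microbial attachment and removing biofilm. On that account, organisms in the VeraFlo arm may rinse away more easily, adding a bias in the same direction.

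It can also be said that a 20-patient pilot should not be judged on false positives. That has some force, but the protocol does fix a significance threshold and does list this endpoint as primary.

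None of this removes the asymmetry. Killing organisms in the wound is the treatment effect; inhibiting them after sampling is not, and the protocol states nothing that keeps the two apart.

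**Conclusion.** The point holds in conditional form. The text establishes one-arm exposure, sampling after dressing removal, an agent described as remaining active in wound material, no stated neutralisation, and a primary endpoint read from that culture. It follows that any carryover would favour Prontosan and could not be distinguished from benefit. It does not follow that carryover occurs, or how often.

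The size is therefore a sensitivity figure, not an estimate: about 5% rising to 10.7% to 15.3% if half of the VeraFlo cultures read one category low, under the assumed distributions and with a post-dressing culture as the endpoint. The change is worth making because it is cheap and protects a primary endpoint from an error that could run in only one direction. Confidence is medium.

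**What to change.** In the wound-culture paragraph of Study Design:

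1. State the specimen type.
2. Collect all research cultures, in both arms and in the same way, into a transport medium containing an antiseptic neutraliser agreed with the hospital laboratory. If the laboratory already does this, say so.
3. Record the time from last instillation to sampling.
4. Do not mandate a rinse, since it may remove organisms unequally between arms.

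If neutralisation is not feasible, describe the endpoint as recoverable growth at dressing change, and do not claim from it alone that bacterial load in the wound was reduced.

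The cost is a few lines of text, neutralising media for at most three cultures per patient, and a check that the medium suits organism identification and susceptibility testing, which the protocol takes from the same cultures. The change concerns measurement only and leaves treatment as it is.

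### Randomisation is fixed at the pre-operative visit, although the arms first differ at the dressing in the OR; a concealed allocation opened just before the dressing would be a cheap improvement

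*Protocol*

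**What the plan says.** All of this stands in the protocol.

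- **Time of randomisation (Study Design):** "The subject will sign consent, be enrolled, and then be randomized at the pre-operative/screening visit".
- **What is allocated (Study Design):** patients "will be enrolled and randomized to either the VeraFlo with Prontosan group or standard negative pressure group". Both arms receive NPWT at 125 mmHg; the device and dressing, with or without Prontosan instillation, follow the allocation.
- **When the arms separate (Study Design):** "All NPWT dressings will be applied sterilely in the OR after debridement and irrigation per standard of care practice".
- **Cultures (Study Design):** bacterial load is obtained "via semiquantitative wound culture(s) done at each debridement procedure", and "A maximum of 3 wound cultures will be used for the purposes of research". The sample is taken in the OR before the surgical prep, and the hospital laboratory reports the quantity.
- **First operation (Study Design):** "During the initial surgical debridement procedure, information about the wound characteristics, the wound culture results" and details of the dressing are recorded for research.
- **Endpoints:** bacterial load and time to wound and fracture healing are primary; the number of operative debridements until the wound has healed is secondary.
- **Eligibility (Inclusion/Exclusion Criteria):** "Patients who will be undergoing surgical management (including the use of NPWT therapy". NPWT is thus planned, but not yet started, when the patient is randomised.
- **Withdrawal of Subjects:** "The Investigator(s) may elect at any time to withdraw a subject from the study for any reason unrelated to the study", on condition that this serves the subject's medical interest. Follow-up data are still to be sought and the reason recorded.

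The protocol does not describe how the allocation is concealed, who learns it or when, or any masking.

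**The concern.** Nothing done before the dressing depends on the arm, yet the arm is fixed before any of it happens. Two things are at stake.

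**Knowledge of the arm before treatment starts.** If those in the OR know the arm, it can influence how the wound is sampled, how it is described and how extensive the first debridement is. The initial culture is the only bacterial-load reading that shows whether the arms started alike. The first debridement may itself bear on wound healing and on the number of later debridements. A difference between the arms in how it was done could not be told apart from an effect of the instillation.

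**Patients randomised but never given NPWT.** If the plan changes at surgery, the patient already belongs to an arm. Kept in that arm, the patient contributes an outcome that the study dressing could not have affected. Left out, the groups are no longer those that were randomised, and the decision to leave the patient out may have been made with the arm known.

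**Working it through.** The plan gives no figure to reproduce on this point: the study calls itself a pilot and makes no power claim. The check is the order of events, followed by the size of the possible dilution.

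**Order of events at the first operation**

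| Step | Where and when | Depends on the arm? |
|---|---|---|
| Consent, enrolment, randomisation | Pre-operative/screening visit | – |
| Initial culture | OR, before the surgical prep | No |
| Wound description | OR, initial debridement | No |
| Debridement and irrigation | OR | No |
| Dressing applied | OR, after debridement and irrigation | Yes, the first step that does |

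The sentence on culture timing refers to removal of a negative pressure dressing, which fits the later changes best. That there is an initial culture follows from two other statements: cultures are done at each debridement, and culture results are collected at the initial one.

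**Share of the culture data concerned.** At most 3 research cultures are used per subject, and at least one further debridement is planned. The initial culture is therefore 1 of 3, or 1 of 2 where only one further debridement is done.

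**Weight of one subject.** With 10 per arm, one subject is 1/10 = 10 percentage points of an arm.

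**Dilution if patients without NPWT stay in their assigned arm.** Assumptions: k of 10 in each arm do not receive NPWT, and their outcome does not depend on the arm. Then

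observed difference = true difference × (10 − k)/10.

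The documents give no rate of loss between the visit and the dressing, so k = 0, 1, 2 is an assumed range. The true difference of 30 percentage points in the proportion healed at a time point is only an illustration.

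| k per arm | Factor | Dilution | 30 points becomes |
|---|---|---|---|
| 0 | 10/10 | 0% | 30 |
| 1 | 9/10 | 10% | 27 |
| 2 | 8/10 | 20% | 24 |

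**Under later allocation.** If the arm is opened once NPWT is confirmed, just before the dressing, patients who do not proceed to NPWT are not randomised. This source of dilution disappears, and the culture, description and debridement are complete before anyone can know the arm.

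**The case against.** The strongest objection is that no error is shown. Randomising before surgery is consistent with the rest of the protocol and does not invalidate the comparison. Early disclosure would cause the bias, not early assignment: an assignment made at the visit and kept sealed until the dressing would protect the culture and the first debridement equally well. This is right as far as it goes. It does not cover the second problem, because a sealed assignment still leaves patients who never receive NPWT in the randomised set.

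The initial culture also precedes treatment, and the protocol's analysis section names a rank sum test without saying how that culture enters. Its effect on the treatment comparison therefore cannot be quantified from this document. That stands; the route through the first debridement does not depend on it.

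A reader might infer more than the documents support in four places:

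- **That the surgical team knows the arm.** The protocol does not say so. Its silence leaves the possibility open and no more.
- **That the reported bacterial category is biased.** The hospital laboratory reports the quantity, so the reading is less exposed than the sampling. It is not immune, since a changed sample can change the category and the laboratory is not said to be masked.
- **That investigators may remove patients freely once the arm is known.** Withdrawal is limited to reasons unrelated to the study and to the subject's medical interest, with follow-up still sought.
- **That early losses must shrink the trial.** Up to 30 may be enrolled for 20 completed, so subjects left out can be replaced. A loss of precision computed from a fixed 10 per arm need not occur.

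**Conclusion.** The point holds as a worthwhile design improvement, not as a contradiction or a fatal flaw. The protocol places randomisation earlier than the design needs. This exposes the only pre-dressing bacterial-load measurement, the wound description and the first debridement to possible knowledge of the arm, and it makes early non-recipients of NPWT part of the randomised set.

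The size is modest. The exposed culture is 1 of 2 or 1 of 3 per subject. Dilution is 10% or 20% if 1 or 2 of 10 per arm do not receive NPWT and are kept in their arm. Those counts are assumed; because NPWT is planned at inclusion, the true number should be small and may be zero. The bias from knowledge of the arm is a risk that the documents neither confirm nor exclude, and no size can be put on it.

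**What to change.** Replace the sentence on consent and randomisation in Study Design with:

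*Consent and screening take place at the pre-operative visit. A concealed allocation is opened in the OR after the initial culture and debridement, once NPWT is confirmed and just before the dressing is applied. Patients who do not proceed to NPWT are not randomised and count as screen failures.*

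This fits Study Recruitment, which already leaves screen failures out of its count of 20.

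The cost is small but real: the wording change, a sealed or electronic allocation available in the OR, and both dressing systems at hand for each case. No extra patients or visits are needed.

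The change protects only what comes before the first dressing. Later cultures, later debridements and follow-up remain open.
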